## **16.0 Costs/Payments to Subjects**

The only cost that the subjects may be responsible for in this study is the cost of transportation to and from the appointments.

Compensation will not be provided, however, RESTASIS will be provided at no charge to the subject by AbbVie, Inc and the PURILENS will be provided at no charge by Lifestyle, Inc.

## **17.0 Compensation for Research-Related Injury**

If there is an ocular injury in this study directly related to the study, treatment for the injury and any subsequent referrals will be covered by the study. The subject will not receive any direct compensation. If there is an unrelated or non-ocular injury during a subject's enrollment in the study, it will not be covered by the study

## **18.0 Confidentiality**

The subject ID worksheet, informed consent, subject surveys, and examiner worksheets will all be kept in a single binder, locked in the office of the principal investigator. The informed consent forms and the subject ID worksheet will be kept in a separate binder from the study data.

At the start of participation in the study, the subject will be assigned a non-identifiable subject ID that will be used for identification on all other documents used in the study. This identification document, which will be the only document that decodes the subject, will be kept in a locked filing bin in a locked room within BostonSight, separate from the informed consent and other study documents. Names, email addresses, and telephone numbers will be recorded in this subject ID worksheet, which will be a paper file kept in the locked office of the principal investigator.

All other exam findings will be recorded on the paper forms and stored in a binder. This binder will be kept locked in the clinical research coordinator's office when not being used to add or remove data collection worksheets.

Only the investigators will have access to the paper and electronic records kept in this study.

All study data will be stored for a minimum of 3 years following study completion. The link will be maintained to allow pertinent regulatory or government agencies to inspect the data and ensure that subjects participated in the study. The principal investigator will be responsible for maintaining study data security and subject confidentiality.

## **19.0 Provisions to Protect the Privacy Interests of Subjects**

We will ensure that all data is maintained with confidentiality and will assure subjects of this when they begin the study. If subjects are not comfortable with disclosing any of the information that is asked in the study, they will not be pressured to disclose, but they may not be able to participate if the withholding prevents us from screening or determining eligibility in the study. All PHI (DOB, name, health information) will be stored in the locked office of the Principal Investigator.

Subjects will only be asked questions that are relevant to the study and their ocular health. The investigators, who are all optometrists that regularly see patients and communicate about potentially sensitive information, have been trained to develop proper rapport with patients and study subjects. All investigators will make every effort to avoid seeming intrusive when asking the subjects questions.

## **20.0 Informed Consent Process**

Informed consent will be obtained before any testing is done. The subject will be provided an informed consent document written in non-technical language. The study staff will review the document with the subject and will give the subject adequate time to review the form and ask any questions before deciding whether to participate. After answering any questions, if the study staff believes the subject comprehends the elements of the informed consent document, the study staff will invite the subject to participate in the study and will have the subject sign the consent form. The investigators and key personnel associated with the informed consent process are trained to not influence the participant in their decision to participate in the research or not. The individual may choose not to sign the consent form without any coercion from the study personnel. Non-participation in the study from patients will not impact future care. Informed consent is estimated to take approximately 30 minutes for this study.

## **21.0 Process to Document Consent in Writing**

Participants will complete the Informed Consent document.

## **22.0 HIPAA**

Study will be performed in compliance with HIPAA regulations. Subjects will be asked to sign a HIPAA Authorization to allow access to their private information.

## **23.0 Data Management**

Data will be stored in a study paper file at BostonSight. Electronic data will be stored on a password-protected computer in a locked office. All study data will remain at BostonSight for a minimum of 3 years following study completion. The principal investigator will be responsible for maintaining study data security and subject confidentiality, and the PI and the study

coordinator will be responsible for receipt and transmission of the data. The investigative team, study sponsor and inspectors from regulatory agencies such as the US Food and Drug Administration will have access to the data if requested for study monitoring or an audit.

All collected data will be documented on study documents and analyzed for differences between baseline and test data. Hypothesis testing will be performed using statistical analyses including parametric or nonparametric comparisons (i.e., t-tests, signed-rank tests), analysis of variance, general linear models, correlation, or regression techniques.

#### **24.0 Specimen Use and Banking – N/A**

#### **25.0 Sharing of Results with Subjects**

Study results will not be shared with subjects, unless the investigator feels that the subject should know something about the ocular health of their eye as a result of the study.

#### **26.0 Resources**

All investigators in this study are optometrists or ophthalmologists and are qualified to examine subjects and evaluate the performance of the PROSE devices. The investigators all have experience working within BostonSight, and with all the exam rooms, equipment, and data storage rooms. All investigators have completed the necessary training for good clinical practices and are specialists in lens fitting and management. The study coordinator is an experienced coordinator who is also trained on IRB practices and is experienced with informed consent processes and confidentiality.

We do not expect to have difficulty recruiting subjects in this study. All subjects will come from current patients of BostonSight.

BostonSight is the research sponsor and is covering all costs of the study, AbbVie, Inc is providing the study drug (Restasis) no charge. Additionally, Lifestyle, Inc is providing Purilens at no charge.

**Novel Use of Cyclosporine Ophthalmic Emulsion 0.05% in a PROSE Device**

**NCT#: NCT04918823**

**Version: 8/27/2024**

## Statistical Analysis

Statistical analysis was performed using Visual Studio Code (Microsoft Corp., Redmond WA) with python version 3.9.12. Subject data post-treatment was compared to their baseline data, collected prior to initiating use of the study drug. For Group A, the data collected at Visit 1A was considered to be their baseline data pre-intervention. For Group B, the data collected at Visit 1B was considered to be their baseline data (post-initiation of Purilens and pre-initiation of cyclosporine). The core algorithm used was based on statistical functions module `scipy.stats`. For univariate data analysis (before/after visits), paired t-test was performed since every patient received treatment. Paired t-test was conducted by `scipy.stats.ttest_rel` and <https://www.statskingdom.com/paired-t-test-calculator.html>. For bi-variate data, two-way ANOVA (Analysis of variance) was performed. Two-way ANOVA was conducted by `sm.stats.anova_lm(model)` function. The significance level was set to a P-value of  $\leq 0.05$  in all instances of analysis.

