**[contact]**

**[[contact]](mailto:[contact])**

## **1.0 Objectives**

The goal of this prospective observational pilot study is to evaluate the tolerability and safety of RESTASIS (cyclosporine ophthalmic solution 0.05%) when added to the PROSE (Prosthetic Replacement of the Ocular Surface Ecosystem) lens reservoir in patients with ocular surface disease (OSD). Secondary endpoints include early (1-month) efficacy data for ocular signs and symptoms.

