### **3.0 Inclusion and Exclusion Criteria**

The participant will be eligible to participate if the following criteria apply:

1. Written Informed Consent has been obtained prior to any study-related procedures taking place
2. Subject is Male or Female, 18 years of age or older prior to the initial visit
3. Is an established wearer of PROSE devices for > 6 months in both eyes

4. Has a finalized PROSE lens design in both eyes, in the opinion of the clinician
5. The PROSE design does NOT include fenestrations
6. Subject requires PROSE devices to treat symptoms and/or signs from underlying dry eye disease, GVHD, Sjogren's syndrome, limbal stem cell deficiency, keratoconjunctivitis sicca, or ocular surface disease
7. Baseline Corneal staining grade of 2 or higher in total, both eyes combined (NEI Grading System)
8. Baseline Ocular Surface Disease Index 13 or greater
9. In the opinion of the investigator, the subject can follow study instructions
10. In the opinion of the investigator, the subject can complete all study procedures and visits
11. Able to wear PROSE device continuously for at least 6 hours at a time without removal, in each eye
12. Able to wear PROSE device for at least 10 total hours a day, in each eye
13. Able to wear PROSE device in subsequent continuous sessions of 6 hours, followed by a break to re-instill Restasis in device bowl, followed by another period of continuous wear of at least 4 hours
14. Currently using buffered preservative free normal saline (Purilens) in the device bowl or willing to transition to buffered preservative free normal saline (Purilens) use in the device bowl during the study

The participant would NOT be eligible to participate if at least one of the following criteria is met:

1. Is currently participating in any other type of eye-related clinical or research study
2. Is pregnant or nursing as reported by the subject.
3. Has a condition or is in a situation which, in the investigator's opinion, may put the subject at significant risk, may confound study outcomes, or may significantly interfere with the subject's participation in the study.
4. Has had previous ocular surgery within the past 12 weeks.
5. Currently uses or has a prior history of using Restasis in the last 3 months
6. Currently uses or has a prior history of using Cequa in the last 3 months
7. Is currently using Xiidra and has been using Xiidra for less than 3 months

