#### **5.0 Number of Subjects**

This study will enroll a minimum of 10 subjects. We expect an approximate 10% drop-out rate, so we will expect to recruit approximately 12 subjects; and the first 10 to be eligible and complete the study will be used for data analysis. All subjects will receive the study drug, Restasis (cyclosporine ophthalmic solution 0.05%).

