#### **7.0 Multi-Site Research Communication – N/A**

#### **8.0 Study Timelines**

The total duration of the subjects' participation in the study will be between 4-6 weeks. It is anticipated that to enroll all study subjects, it will take approximately 8 months. The estimated date for completion of this study is 12 months after the start of recruitment.

The study will enroll 2 groups of subjects:

- Group A: Those subjects already using preservative free buffered normal saline (Purilens) at the time of enrollment to the study

- Group B: Those subjects NOT currently using preservative free buffered normal saline (Purilens) at the time of enrollment but who are willing to be switched to preservative free buffered normal saline (Purilens) as part of the study protocol

Visit 1A:

- a. Completion of informed consent
- b. Collect past medical history, past ocular history, allergies, medications as well as habitual contact lens information, including lens design, power, and diameter.
- c. Subject's evaluation of symptoms via a baseline tolerability questionnaire and baseline Ocular Surface Disease Index (OSDI)
- d. Visual acuity assessments of both eyes (logMAR)
- e. Baseline assessment of PROSE device:
  - a. Confirm acceptable fit
- f. Baseline Oculus Keratograph 5M R-Scan with lens (automatic classification of redness)
- g. Remove lens
- h. Baseline Oculus Keratograph 5M R-Scan without lens (automatic classification of redness)
- i. Baseline slit lamp examination (without lens) including:
  - a. anterior segment and ocular surface
  - b. conjunctival redness (Efron Grading Scale, Modified Efron Grading Scale)
  - c. corneal staining with sodium fluorescein (NEI Grading System)
  - d. conjunctival staining with lissamine green (NEI Grading System)
- j. Initiation of study, with either:
  - a. Group A (subjects currently using Purilens): Dispense Restasis for initiation of usage in device bowl
    - i. Instructions for use: 1 drop of RESTASIS in the lens bowl followed by filling the remainder of the lens bowl with Purilens qAM. After 6 consecutive hours of wear, remove and reapply lens with 1 drop of RESTASIS in the lens bowl followed by filling the remainder of the lens bowl with Purilens. Wear lens without removal for at least 4 more consecutive hours.
  - b. Group B (subjects NOT currently using Purilens): the subject will be provided Purilens for use over the next two weeks and return for Visit 1B
- k. Reapply lens and wait 15 minutes

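### Does pooling Group A's entry-visit baseline with Group B's re-measured baseline, and leaving Group B's earlier pre-drug readings unused, require a change to the SAP?

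*SAP*

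**What the plan says.** The treatment side is simple: "All subjects will receive the study drug" (Protocol 5.0), and the first 10 eligible completers are analysed. There is no control arm. The SAP compares post-treatment readings with baseline by paired t-test at P ≤ 0.05.

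The baseline depends on which saline the subject was using at enrolment:

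- Group A, already on Purilens: "For Group A, the data collected at Visit 1A was considered to be their baseline data pre-intervention".
- Group B, not yet on Purilens: "For Group B, the data collected at Visit 1B was considered to be their baseline data (post-initiation of Purilens and pre-initiation of cyclosporine". At Visit 1A, "the subject will be provided Purilens for use over the next two weeks and return for Visit 1B" (Protocol 8.0). OSDI, tolerability questionnaire, acuity, R-Scan and slit-lamp grading are all repeated at 1B before the drug is dispensed.

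Two endpoints are also entry thresholds (Protocol 3.0): "Baseline Ocular Surface Disease Index 13 or greater" and "Baseline Corneal staining grade of 2 or higher in total, both eyes combined".

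On any further analysis the SAP says only "For bi-variate data, two-way ANOVA (Analysis of variance) was performed". It names no factors, no display by group and no use of Group B's Visit 1A readings. Efficacy is secondary: "Secondary endpoints include early (1-month) efficacy data for ocular signs and symptoms" (Protocol 1.0). The Statistical Analysis text in Protocol 10.0 presents the study as a small, mainly observational pilot about tolerability.

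**The concern.** When a subject must exceed a threshold to enter, and the qualifying reading is also the baseline, part of any later fall is regression to the mean. Group A is in that position. Group B is re-measured at 1B, so its baseline is largely free of the selection. One paired test therefore pools two kinds of baseline, and the non-drug part of the average change depends on the mix of A and B, which the documents do not give.

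Group B's change from 1A to 1B is the only off-drug movement the study records, and the SAP gives it no role. With no control arm and a P ≤ 0.05 rule on early efficacy, a reader could take a regression artefact for improvement. Protocol 8.0 also uses the word baseline at both visits, which at first leaves open which one decides entry.

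**Working it through.** **1. Which visit decides entry?** Three places in the Protocol bear on this.

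- Inclusion criterion 14 (3.0) accepts current Purilens users or those willing to move to it. That test makes sense only before the switch.
- Section 8.0 forms the groups by saline use at enrolment and starts Group B's switch at Visit 1A.
- The Visit 1B list contains no eligibility step, and 10.0 labels Visit 1A the initial evaluation.

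Together they place eligibility at 1A. Calling both visits baseline is loose wording.

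**2. The plan's own figure.** The only sample-size arithmetic is recruitment: 10 completers at 10% drop-out gives 10/0.9 = 11.1, rounded up to 12. This reproduces. There is no power statement, effect size or SD to check.

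**3. Size of the artefact on OSDI.** The documents give no OSDI mean, SD or repeatability. Assumed ranges: mean 20, 30 or 40; SD 15 or 20; visit-to-visit correlation r = 0.6, 0.7, 0.8 or 0.9. This makes 24 settings. With cut 13 and a = (13 − mean)/SD,

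expected fall = (1 − r) × SD × φ(a) / (1 − Φ(a)).

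Worst setting (mean 20, SD 20, r = 0.6): a = −0.35, φ/(1 − Φ) = 0.3752/0.6368 = 0.589, fall = 0.4 × 20 × 0.589 = 4.71 points.

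Mildest setting (mean 40, SD 15, r = 0.9): a = −1.80, φ/(1 − Φ) = 0.0790/0.9641 = 0.0819, fall = 0.1 × 15 × 0.0819 = 0.12 points.

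| Mean, SD | r=0.6 | 0.7 | 0.8 | 0.9 |
|---|---|---|---|---|
| 20, 15 | 3.16 | 2.37 | 1.58 | 0.79 |
| 20, 20 | 4.71 | 3.54 | 2.36 | 1.18 |
| 30, 15 | 1.45 | 1.08 | 0.72 | 0.36 |
| 30, 20 | 2.77 | 2.08 | 1.39 | 0.69 |
| 40, 15 | 0.49 | 0.37 | 0.25 | 0.12 |
| 40, 20 | 1.41 | 1.06 | 0.70 | 0.35 |

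The median is 1.13. Of the 24 settings, 17 are under 2 points and 3 are over 3. In the mean 20, SD 20 row a normal curve puts 16% of a 0–100 score below zero. Without that row the maximum is 3.16 and the median 0.92.

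Group B's expected artefact after 1B is about zero, so a 5:5 split halves the pooled shift: 0.12/2 = 0.06 to 4.71/2 = 2.4 points.

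**4. Effect on the test.** Simulated chance of a significant improvement with no true change (paired t-test, n = 10, 200,000 trials; nominal 2.5% in that direction):

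| Mean, SD, r | 0 in Group A | 5 in A | 10 in A |
|---|---|---|---|
| 20, 20, 0.6 | 2.6% | 5.7% | 11.9% |
| 20, 20, 0.8 | 2.5% | 4.5% | 7.9% |
| 30, 15, 0.7 | 2.6% | 3.3% | 4.5% |
| 40, 15, 0.9 | 2.5% | 2.6% | 2.8% |

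The last column requires an empty Group B, so there would be no 1A-to-1B change to report.

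**5. Would a by-group display show it?** After selection, SD of change = √[(1 − r)² × Var(X | X ≥ 13) + SD² × (1 − r²)]. The 95% half-width is t(0.975, n−1)/√n times that SD: 2.48 at n = 3, 1.24 at n = 5, 0.92 at n = 7. At n = 5 this is 8.2 to 21.6 points. In the worst setting it is 20.95 against 4.71, a ratio of 4.4. In the mildest it is 8.30 against 0.12, a ratio of about 68. The median ratio is 12.

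**The case for a change.** The strongest reply is that the case does not rest on the size of one artefact. The plan tests efficacy at P ≤ 0.05 with no control, and any non-drug drift can produce a positive result. By the non-central t distribution, a drift of 0.5 SD of the change, common to all 10 subjects, would be called significant 29.3% of the time. Group B's 1A readings are already scheduled, and listing them costs a few rows. The ANOVA factors are unnamed, so nobody can tell whether group was examined.

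Much of this stands as description. The SAP is silent on those readings and on display by group, and an uncontrolled change cannot be credited to one cause. What does not stand is that the listing would help with the problem raised. The change from 1A to 1B combines regression with a deliberate change of lens fluid that Group A does not make during the study. It covers two weeks rather than one or four, in a few non-randomised subjects. It is not a measure of drift alone and could not be subtracted. Nor do the documents credit change to cyclosporine alone: Protocol 1.0 and 2.0 frame the question as Restasis delivered in the PROSE reservoir, so a caution on attribution would correct a claim that is not made. The unnamed ANOVA factors are a separate matter of specification.

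**Conclusion.** No change to the plan is needed. Visit 1B is the right baseline for Group B, because it keeps the first two weeks of the saline switch out of the drug contrast. Visit 1A is the only pre-drug visit Group A has. Stating that eligibility is judged at 1A would write down what the Protocol already implies. Reporting Group B's change from 1A to 1B would alter no estimate, test or bias, and the intervals are too wide to confirm or exclude regression to the mean.

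The remaining imperfection is small: a Group A OSDI artefact of about 0.1 to 4.7 points, mostly under 2, and a false-improvement rate of 2.6% to 5.7% with an even split. It bears on a secondary aim of a tolerability pilot. These figures rest on assumed OSDI means, SDs and correlations, a normal approximation, eligibility at 1A and an assumed split. The corneal staining cut, at 2 out of a possible 30 for both eyes, was not quantified, nor was the saline switch.

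If the sponsor wishes to list Group B's values at all four visits, that is an optional, labelled post-hoc description. The confounding with the saline switch should be stated beside it.

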**Visit 2: (1 Week post Restasis dispensing)**

- a. Update past medical history, past ocular history, allergies, medications
- b. Visual acuity assessments of both eyes (logMAR)
- c. Subject's evaluation of symptoms via OSDI
- d. Tolerability questionnaire
- e. Oculus Keratograph 5M R-Scan with lens (automatic classification of redness)
- f. Remove lens
- g. Oculus Keratograph 5M R-Scan without lens (automatic classification of redness)
- h. Slit lamp examination (without lens) including:
  - a. anterior segment and ocular surface
  - b. conjunctival redness (Efron Grading Scale, Modified Efron Grading Scale)
  - c. corneal staining with sodium fluorescein (NEI Grading System)
  - d. conjunctival staining with lissamine green (NEI Grading System)

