Slit-lamp Examination	The participant's front portion of each eye and contact lenses will be examined with a lighted microscope. The participant will be asked to place his/her chin on the chinrest and place his/her forehead against the bar and look straight ahead. The instrument's light will be shined onto the eye to visualize the ocular surface for approximately 2-3 minutes per eye.
Sodium Fluorescein/Lissamine Green	Sodium fluorescein/Lissamine Green staining will be used to evaluate ocular surface damage indicated by cell damage or death and for assessing an open vs closed PROSE device system. Corneal and conjunctival staining will be scored using the NEI Grading System.
R-Scan	Non-invasive imaging modality with automated classification of ocular redness level. Instrument used: OCULUS Keratograph 5M. The participant will be asked to place his/her chin on the chinrest and place his/her forehead against the bar and look straight ahead. The investigator will perform a scan of the eye to obtain an image of the front surface of the eye. The computer will then use an embedded software algorithm to quantify the level of redness on a scale from 0 to 4 in 0.1 increments.
Questionnaires	Subjects will be asked to fill out the following questionnaires: 
 
• Ocular Surface Disease Index (OSDI)
 
• Restasis Tolerability Questionnaire
 

*Figure 2. Table including descriptions of tests*

Statistical Analysis:

Subject data will be compared to their baseline status prior to initiating usage of the study drug. Subjects will be reevaluated at 1 week and 1 month visits and the data will be evaluated and compared to baseline. This is a small preliminary pilot study to evaluate tolerability of this treatment model utilizing Restasis. Given the small number of subjects and given our question of initial tolerability, the predominant nature of the results are observational and meant to provide an early means of addressing the question of tolerability.

The following data will be collected. They are all minimal to no risk.

- Visual acuity
  - Visual acuity will be measured on a Snellen chart and converted to logMAR values
- Tolerability survey
  - The Tolerability Questionnaire involves the subject answer a series of questions to assess their symptoms.
- Ocular Surface Disease Index (OSDI)

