  - The Ocular Surface Disease Index is a validated questionnaire consisting of a group of 12 questions designed to assess symptoms of ocular surface disease. The questionnaire is administered by a trained medical staff member. All questions are answered on a scale of 0 to 4 (or the subject has an option to not answer a question). The end score is then mathematically converted to a 0-100 scale, with 0 being no symptoms and 100 being the most severe symptom score.
- Corneal staining (NEI Grading System)
  - Corneal staining is a routine ophthalmic and optometric test which utilizes Sodium Fluorescein stain on the eye to evaluate the health of the ocular surface. The amount of stain adherent to the ocular surface is then recorded utilizing standardized scales. It is minimal risk, including risk of irritation, redness, burning and stinging.
  - The NEI Grading System is a standardized method for quantifying the level of ocular surface signs noted on slit lamp examination. The scale ranges, in whole numbers, from 0 to 3, in 5 distinct sections on the cornea, with 0 indicating that the particular sign is not present and 3 being the most severe version of that specific sign (ie corneal staining, conjunctival staining, conjunctival redness) being measured. The overall score for one eye's cornea (5 sections on each cornea) ranges from 0 to 15.
- Conjunctival staining (NEI Grading System)
  - Conjunctival staining is a routine ophthalmic and optometric test which utilizes Lissamine Green stain on the eye to evaluate the health of the ocular surface. The amount of stain adherent to the ocular surface is then recorded utilizing standardized scales. It is minimal risk, including risk of irritation, redness, burning and stinging.
  - The NEI Grading System is a standardized method for quantifying the level of ocular surface signs noted on slit lamp examination. The scale ranges, in whole numbers, from 0 to 3, in 6 distinct sections on the cornea, with 0 indicating that the particular sign is not present and 3 being the most severe version of that

specific sign (ie corneal staining, conjunctival staining, conjunctival redness) being measured. The overall score for one eye's conjunctiva (6 sections on each eye's conjunctiva) ranges from 0 to 18.

- Conjunctival Redness (Efron and modified Efron scale)
  - Conjunctival redness involves the visual inspection of the ocular surface by the investigator and grading of the amount of redness on a standardized scale.

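### The SAP names a two-way ANOVA with a single residual, and a paired t-test, for data repeated within 10 subjects, but gives no factors, subject term or rule for the two eyes

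*SAP*

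**What the plan says.** The Statistical Analysis section is the whole SAP. It assigns before/after visit comparisons to a paired t-test (`ttest_rel` and an online calculator). For everything else it says: "For bi-variate data, two-way ANOVA (Analysis of variance) was performed", run with `sm.stats.anova_lm(model)`. No formula, factor, endpoint or row definition follows. P ≤ 0.05 is the significance level for every analysis.

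The nearest the documents come to a unit of analysis is "Subject data post-treatment was compared to their baseline data" in the SAP and "Subject data will be compared to their baseline status prior to initiating usage of the study drug" in protocol section 10.0. Section 23.0 adds only an open list of methods.

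On the data, protocol section 5.0 says "the first 10 to be eligible and complete the study will be used for data analysis". Section 8.0 schedules measurements at baseline, 1 week and 4 weeks, with the R-scan taken both with the lens on and after its removal. Section 10.0 measures acuity in each eye, examines each eye at the slit lamp, and scores staining separately for each eye. Inclusion criterion 7 in section 3.0 does combine the eyes for one measure: "Baseline Corneal staining grade of 2 or higher in total, both eyes combined". That is an eligibility rule and is not carried into the analysis.

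**The concern.** `anova_lm` applied to an ordinary linear model produces one residual line and tests every term against it. That suits independent rows. Here the rows are correlated, because the same 10 people are seen at three visits, in two eyes, and for R-scan in two lens states. Depending on choices the SAP does not state, one R-scan analysis could have 10 × 3 = 30 rows, 30 × 2 = 60 (two eyes or two lens states), or 60 × 2 = 120.

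The choices err in opposite directions. If subject is left out, stable differences between people swell the residual. Tests of visit then usually become too strict, and a real worsening of redness, staining or acuity can be missed in a study about safety and tolerability. If subject is added but subject-by-visit variation is not separated, or if eyes are counted as independent pairs, the error can be too small and false positives rise. A reader given only P ≤ 0.05 cannot tell which applies.

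OSDI is one value per subject and no per-eye tolerability score is described, so the two-eye question does not reach those endpoints. The ANOVA question still does.

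**Working it through.** **Inputs from the documents.** 10 analysed subjects (protocol 5.0), three visits (8.0), two eyes, R-scan with and without lens (8.0), nominal level 0.05 (SAP). The only sample-size figure is recruitment: 10 / (1 − 0.10) = 11.1, rounded up to 12, which agrees with section 5.0. There is no power calculation and no stated error rate to reproduce.

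**Assumptions.** The documents give no correlations or variance components, so all of those below are assumed. Visit by lens is used as an illustration because R-scan has that structure; the SAP does not say lens was a factor. Rates come from simulated normal data with no true effect (40,000 trials per ANOVA setting, 100,000 per t-test setting).

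**1. Visit by lens, 10 × 3 × 2 = 60 rows, interaction fitted.** Let the variance shares be S (subject), V (subject-by-visit), L (subject-by-lens) and E (residual), with total 1. With no visit effect:

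- expected mean square for visit = E + 2V
- expected residual, subject omitted (54 df) = S + V + L + E = 1
- expected residual, subject added (45 df) = [54(S+V+L+E) − 9(6S+2V+3L+E)] / 45 = 0.8V + 0.6L + E

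A valid test needs a ratio of visit mean square to residual of 1.

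| S / V / L / E | Ratio, subject omitted | Visit error | Ratio, subject added | Visit error |
|---|---|---|---|---|
| .7/.1/.1/.1 | 0.30 | 0.1% | 0.30/0.24 = 1.25 | 9.2% |
| .6/.1/.1/.2 | 0.40 | 0.3% | 0.40/0.34 = 1.18 | 7.9% |
| .5/.2/.1/.2 | 0.60 | 1.4% | 0.60/0.42 = 1.43 | 12.0% |
| .4/.3/.1/.2 | 0.80 | 3.3% | 0.80/0.50 = 1.60 | 15.2% |
| .3/.3/.2/.2 | 0.80 | 3.1% | 0.80/0.56 = 1.43 | 12.1% |
| .3/.1/.1/.5 | 0.70 | 1.8% | 0.70/0.64 = 1.09 | 6.4% |
| .5/0/0/.5 | 0.50 | 0.6% | 0.50/0.50 = 1.00 | 4.9% |
| .2/.5/.1/.2 | 1.20 | 8.9% | 1.20/0.66 = 1.82 | 18.8% |

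Over the same cases the lens test runs at 0.6% to 3.4% with subject omitted and 2.7% to 12.6% with subject added. A repeated-measures ANOVA (`AnovaRM`), which tests visit against subject-by-visit variation, gives 5.0% to 5.1% for visit and 4.8% to 5.2% for lens.

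**2. Visit alone, one row per subject-visit (30 rows).** With within-subject correlation r and subject omitted, the ratio is 1 − r. At r = 0.3, 0.5, 0.7 and 0.8 the error is 1.9%, 0.5%, 0.1% and 0.01%. Where the subject + visit model has 80% power, this one has 67%, 47%, 20% and 7%. With subject entered, the error is 4.8% to 5.2%.

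**3. Paired t-test on 20 eyes.** If the two eyes' changes correlate at ρ, the variance of the mean is (1 + ρ)/20 in units of the variance of one eye's change. The test estimates it as (1 − ρ/19)/20. At ρ = 0.5 the understatement is 1.5/0.974 = 1.54-fold.

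| ρ | 0 | 0.1 | 0.2 | 0.3 | 0.5 | 0.7 | 0.9 |
|---|---|---|---|---|---|---|---|
| 20 eyes | 5.0% | 6.2% | 7.3% | 8.5% | 11.2% | 14.2% | 16.9% |

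On 10 two-eye means the error is 4.9% to 5.1% throughout.

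**4. A Group A/B factor, if one was used.** With an assumed 5/5 split, 30 rows and no subject term, the group ratio is 1 + 2r. At r = 0.3, 0.5 and 0.8 the error is 11.8%, 16.4% and 22.8%.

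**5. Limit of the remedy.** With unequal correlations between visits, the uncorrected `AnovaRM` visit test runs at 5.7% to 7.7%. The subject-level paired t-test stays at 5.1%.

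**The case against.** The strongest reply is that the SAP may describe a sound analysis tersely. Subject + visit in `anova_lm`, with one row per subject-visit, is itself a two-way ANOVA. It is valid when the differences between visits have equal variance (sphericity). Both documents speak of each subject's data against that subject's own baseline, which leans towards the subject as unit. This stands, and it is why the point is about what is unspecified and not about a demonstrated error. It does not supply an eye rule (mean, total, worse eye or one eye), the factors or the error term.

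A reader might infer that eyes were analysed as independent pairs, or that subject was left out. Neither is shown. A reader might also say the ANOVA is valid only with one row per subject-visit. That is too strong: in the .5/0/0/.5 case, two rows per subject-visit with subject added gives 4.9%.

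Nor do the documents settle whether Groups A and B were compared. Section 8.0 defines them and the SAP gives each its own baseline, but neither states or rules out a group factor.

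It is also fair to say that the visit-by-lens figures illustrate a hypothetical model for one of seven endpoints, and that lost power is not universal. Where `AnovaRM` has 80%, the model without subject has 22% to 76% in the first six cases and about 50% and 89% in the last two. The 89% belongs to the case with inflated error.

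**Conclusion.** The concern holds as a gap in specification joined to a named method that generally has the wrong error term for these data. Unless the model was subject + visit on one row per subject-visit, the nominal 5% is not dependable. Under the assumed variance shares, visit tests run at about 0.1% to 3% without subject (about 9% with large subject-by-visit variation) and 5% to 19% with subject merely added. Paired t-tests run at 5% to 17% if the 20 eyes were the pairs and ρ lies between 0 and 0.9. A group factor tested without between-subject error would be too liberal.

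These ranges rest on normal data and assumed correlations. They show what the unstated choices could do, not what happened. The documents do not support concluding that any reported p-value is wrong.

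The consequence is limited. Section 10.0 calls the results predominantly observational, and no decision rule depends on the ANOVA. The point should still be fixed, because the SAP applies P ≤ 0.05 to every analysis.

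**What to change.** - State that the subject is the unit, and give the rule for combining the two eyes before each test. One option is the both-eye total for staining, following inclusion criterion 7, and the two-eye mean for acuity, redness grade and R-scan. Other rules would serve if stated.
- Name the two factors and the endpoints of each ANOVA, and give the formula.
- For visit alone, use `AnovaRM` or subject + visit with one row per subject-visit. For visit and lens together, use `AnovaRM` in place of a plain two-way `anova_lm`; adding subject to `anova_lm` is not enough there.
- Report subject-level paired t-tests of each visit against baseline beside it, since `AnovaRM` needs complete data and has no sphericity correction.
- Test any group factor against between-subject error.

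The SAP is written in the past tense, so re-running should depend on what was done. If the analysis already met these terms, a short clarification closes the point. If not, only the affected tests are repeated. The cost is SAP wording and a few lines of code in the same Python libraries, with no new data. Some p-values may move in either direction.
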